We developed the first dyadic skills-based intervention – Recovering Together - to prevent chronic heightened emotional distress in at risk ANI pt-cg dyads. The “Recovering Together” program is informed by the theoretical response-shift framework of adaptation to acute illness⁵³ (successful adaptation implies recalibration of values and life goals), the family strength vulnerability model²⁴ (within dyads relational systems have strengths and weaknesses in how they cope with life events), the dyadic longitudinal model²² (distress travel from one member of the dyad to the other across time), the APIM model⁵⁴, and the resiliency framework¹⁷. The program is in line with recent recommendations for skill-based interventions for critical care patients, and uses preliminary data collected by our team for the past 3 years^{4, 13-15}. The intervention teaches pts and cgs resiliency factors that are associated with well-being after trauma for both pts and cgs: *mindfulness* – the ability to stay present and defer judgment in the face of adversity¹⁸; *coping* – the arsenal and application of one’s behavioral, cognitive, and emotional strategies to manage stress¹⁹; *social support* –empathetic interpersonal interactions that meet one’s emotional and functional needs²⁰; *self-efficacy* – perceived ability to adapt under adversity²¹ and *positive dyadic interpersonal communication to increase interpersonal bond*¹². Informed by the aforementioned theoretical models, our conceptual model hypothesizes that by teaching both members of the dyad resiliency and interpersonal communication skills (e.g., Recovering Together) we will be able to sustainably decrease emotional distress in both members of the dyad

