In addition, our team has an established record of collaboration on published or ongoing investigations. **Emotional distress is prevalent in dyads, interdependent between pt and cg, and negatively associated with resiliency factors**⁴. Our team conducted a cross-sectional study of pt-cg dyads in the NICU (40% stroke, 30% tumor). 75% pts and 84% cgs approached agreed to participate. 74% pts had been intubated at one time during NICU admission, and 2/3 were discharged home. Rates of clinically significant symptoms of depression, anxiety and PTS did not differ between pts (24%, 43%, 21%) and cgs (24%, 46%, 17%), or by any demographic or medical characteristic. Dyadic modeling showed that for both pts and cgs, mindfulness and coping impacted both self and partner’s emotional distress symptoms. We showed: 1) feasibility of recruitment; 2) high emotional distress in dyads; and that 3) modifiable resiliency factors (mindfulness and coping) are intervention targets interdependently associated with distress in pts and cgs, regardless of the identity of cg (e.g., spouse, friend, etc).

Resiliency factors are associated with lower emotional distress in NICU dyads¹³. Our team found that resiliency factors of mindfulness, coping, self-efficacy and patient-caregiver interactions were associated with decreased emotional distress in dyads of ANI. This study confirms mindfulness, coping as intervention targets and provides novel evidence on self-efficacy and patient-caregiver interaction as additional important intervention targets.

ANI pts have greater anxiety than cancer patients at early diagnoses¹⁴. We led the first cross-comparison study of emotional distress among dyads with ANI and cancer. This study supports the priority of addressing emotional distress in ANI dyads as has been emphasized for cancer dyads.

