Clinically significant emotional distress in one member of the dyad at hospitalization predicts chronic emotional distress in at least 1 of the dyad members 3 and 6 months later⁵⁵. Our team has an ongoing prospective study of dyads with ANI. Retention rates for dyads due for assessments at 3 and 6 months thus far are 84% and 91% for pts and 87.7% and 95.7% for cgs, confirming our ability to retain post-ANI participants. Within each dyad, if one member screens in for clinically significant symptoms for any diagnosis (i.e., depression, anxiety or PTSD) at hospitalization there is good sensitivity and specificity that one member of the dyad will endorse clinically significant symptoms 3 months later. This study shows a reliable method for identifying dyads of patients at risk for chronic heightened emotional distress by identifying dyads in which either the pt or cg screens in for heightened emotional distress (symptoms of depression, anxiety or PTSD).

Caregiver gender moderates the prospective association of resiliency factors to emotional distress⁸⁷. This study found that at the time of admission resiliency factors have main effects on emotional distress, with no differences by cg gender. However, significant interaction effects emerged prospectively such that male cgs with high mindfulness at baseline demonstrated lower levels of emotional distress at 3 and 6 months later than did males with low mindfulness ($p = 0.026$ and $p < 0.013$). Similarly, women cgs with high intimate bond at baseline reported the lowest levels of depression symptoms 3 and 6 months later ($p < 0.020$). This study confirmed the need to assess and address resiliency factors early in the recovery process, and identified important gender differences to be accounted for in intervention development.

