implementation and scalability of the intervention including nurse involvement. Nurses concurred with pts experiences, and suggested strategies to recruit and retain dyads for the study, which are now included in the methodology section of the current grant proposal. Studies 3.6 and 3.7 represent the building blocks for the development of our Recovering Together program and manual. Nurses provided edits and contributed to the iterative development of the manual. These studies also confirm feasibility of conducting the pilot RCT proposed through this R21.

II. SPECIFIC AIMS

The current study has the following objectives:

Aim 1: To determine the feasibility of recruitment, feasibility of program delivery, program credibility, and program satisfaction using evidence-based benchmarks.

Hypothesis 1: We hypothesize that > 75% of the dyads approached will agree to participate.

Hypothesis 2: We hypothesize that > 75% of dyads who start the intervention will complete at least 4 sessions.

Hypothesis 3: We hypothesize that > 75% of participants will report average credibility (Credibility and Expectancy Questionnaire) scores greater than the scale's midpoint.

Hypothesis 4: We hypothesize that > 75% participants will report average satisfaction (Client Satisfaction Scale) scores greater than the scale's midpoint.

Aim 2: To demonstrate a proof of concept that the Recovering Together program can sustainably improve emotional distress [Hospital Anxiety and Depression Scale; HADS], Post Traumatic Symptoms (PTS) [PCL-S], resiliency variables (mindfulness, coping, social support and self-efficacy) and interpersonal factors (interpersonal bond).

Hypothesis 1: We hypothesize that participation in the Recovering Together Program will be associated with a more potent decrease in emotional distress and PTS compared to participation in the educational program (control), and that these improvements will maintain at 3 month follow up.

Hypothesis 2: We hypothesize that Recovering Together Program will be associated with a more potent increase in resiliency variables (mindfulness, coping, social support, self-efficacy) and interpersonal factors (interpersonal bond) compared to participation in the educational program, and that these improvements will maintain at 3 month follow up.

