For this feasibility pilot RCT, our primary outcomes (feasibility, credibility and satisfaction) will be assessed in Aim 1. Our secondary outcomes in this trial are: emotional distress, PTS, mindfulness, coping, social support, self-efficacy, and interpersonal bond, and will be assessed in Aim 2.

III. SUBJECT SELECTION

All participants will be recruited from the Massachusetts General Hospital Neuroscience ICU, using IRB approved recruitment materials.

Inclusion/Exclusion Criteria

Eligible dyads (Pts and Cgs) must meet the following inclusion criteria:

- 1) Age 18 or older
- 2) English fluency and literacy
- 3) Access to high speed internet for video sessions
- 4) Pt with an informal cg (family or friend who provides unpaid care) available and willing to participate
- 5) Hospitalized with an ANI within 1-2 weeks (pt) OR primary cg of a pt currently admitted with an ANI
- 6) Either pt or cg have clinically significant symptoms of depression, anxiety, and/or PTS

One or more of the following exclusion criteria will render a pt ineligible:

- 1) Permanent and severe cognitive impairment severe enough to impede participation – This will be determined by trained study staff through an assessment conducted as part of usual care and that includes the MMSE (score of <23) and GCS (score of <10). Nurses and study staff are trained and use these measures as part of NICU care.
- 2) Dyads where the pt is anticipated to die or to never be able to participate due to medical sequelae. This will be determined by nurses.

All adult patients and family caregivers, satisfying all inclusion criteria, are eligible for enrollment in this study regardless of sex, race, or ethnicity. Vulnerable populations will not be recruited.

Recruitment

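### Dyads enter if either member screens positive on any one condition, so members start from mixed baselines; Section VI names no baseline adjustment and does not report the dyad-level at-risk status that defined entry

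*Combined protocol and SAP*

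**What the plan says.** - **Entry (Section III, Inclusion/Exclusion Criteria).** The symptom criterion is "Either pt or cg have clinically significant symptoms of depression, anxiety, and/or PTS". It applies to the dyad. No instrument or cut-off is given with it.
- **Basis for the rule (Section I).** In the team's prospective study, clinically significant distress in one member at hospitalization "predicts chronic emotional distress in at least 1 of the dyad members 3 and 6 months later". The same section says of dyads that screen in that "there is good sensitivity and specificity that one member of the dyad will endorse clinically significant symptoms 3 months later". Predictor and predicted status are both at dyad level.
- **Purpose (Section I).** The program was developed "to prevent chronic heightened emotional distress in at risk ANI pt-cg dyads". The same paragraph closes with a conceptual model in which distress is lowered in both members.
- **Hypotheses (Section II, Aim 2).** Hypothesis 1 is that the program "will be associated with a more potent decrease in emotional distress and PTS compared to participation in the educational program", measured by HADS and PCL-S. Hypothesis 2 predicts increases in the resiliency and bond measures.
- **Outcomes (end of Section II).** Seven secondary constructs are listed. Above-threshold status is not among them, for a member or for a dyad.
- **Analysis (Section VI).** The effectiveness question is followed by an account of how the program was developed, with no test. The durability question gives a within-group t test of 3 months against post-intervention, then t tests and chi-squared tests at 3 months. No baseline adjustment, categorical variable or split by baseline status is named.

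**The concern.** The entry rule and its evidence concern the dyad: is at least one member clinically distressed, now and three months later? The planned outcomes are scores. The rule also brings in people who are below threshold on a given scale, either because their partner qualified the dyad or because they qualified on another condition. The arms are therefore compared on groups with widely spread starting scores, and the plan does not use those scores in the comparison.

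Three things are at stake:

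- precision, in a trial planned to end with 30 dyads per arm;
- the meaning of the effect size for emotional distress, which Section VI names as something the pilot should estimate;
- whether the trial can say that at-risk dyads were kept from chronic distress.

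**Working it through.** **Plan's own figure.** Section VI recruits 40 dyads per arm to keep 30 after 25% attrition: 30/(1 - 0.25) = 40. This reproduces.

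**Inputs.** Section I gives rates above threshold in NICU dyads not selected for distress. For depression, anxiety and PTS they are 24%, 43% and 21% in patients and 24%, 46% and 17% in caregivers. Overlap between conditions and between partners is not reported, so it is varied below.

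**Formula.** Anyone above threshold makes their own dyad eligible. So, given these rates, the share above threshold among enrolled people is exactly p/E, where p is the unselected rate and E the share of dyads that qualify.

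**Values of E.**
- Full overlap: E equals the largest single rate, 46%.
- Six independent screens: E = 1 - (0.76 × 0.57 × 0.79 × 0.76 × 0.54 × 0.83) = 88%.
- Upper limit: 100%.
- Simulation of six correlated screens (500,000 dyads; assumed within-person correlation 0 to 0.85, between-partner 0 to 0.4): E runs from 65% to 88%.

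**Share above threshold among enrolled participants.**

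| E | Depression, both roles | PTS, patients / caregivers | Anxiety, patients / caregivers |
|---|---|---|---|
| 46% | 52% | 46% / 37% | 93% / 100% |
| 65% | 37% | 32% / 26% | 66% / 71% |
| 88% | 27% | 24% / 19% | 49% / 52% |
| 100% | 24% | 21% / 17% | 43% / 46% |

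Example: 0.24/0.46 = 0.52.

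Across the simulations, roles pooled:
- depression 27-37% above, so 63-73% below;
- PTS 21-29% above, so 71-79% below;
- anxiety 50-69% above.

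Anxiety falls below half only if E exceeds 0.43/0.5 = 86% (patients) or 0.46/0.5 = 92% (caregivers). Section I reports that distress is interdependent within dyads, which pulls E below the 88% of independent screens.

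In the same simulations, 23-35% of enrolled people are below threshold on all three conditions. In 47-70% of enrolled dyads only one member is above.

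**What ignoring baseline costs.** Adjusting for the same scale's baseline score multiplies the residual variance by about 1 - r², where r is the correlation between baseline and follow-up. The documents do not give r, so the gain cannot be put in figures here.

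**What a dyad-level proportion could show.** With 30 dyads per arm, the 95% half-width for the difference is 1.96 × √{[p₀(1 - p₀) + p₁(1 - p₁)]/30}. The rates are assumptions:
- p₀ = 0.6, p₁ = 0.5: 1.96 × √(0.49/30) = 0.25;
- p₀ = 0.8, p₁ = 0.7: 1.96 × √(0.37/30) = 0.22.

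For control rates of 60-80% and two-sided alpha of 0.05 (also assumed), power is 12-14% for a 10-point drop and 34-39% for a 20-point drop. The proportion is an estimate to report, not a test.

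**The case against.** The strongest reply is that the design is deliberate. Section I calls for dyadic interventions that target improvement in both members, and its conceptual model is a sustained decrease in both. Measuring each member, including one whose partner qualified the dyad, follows from that. Both arms complete HADS and PCL-S at all three time points. If control members who began well deteriorate and intervention members do not, the difference in means captures it. For a later trial with the same entry rule, the average over enrolled members is a relevant effect. These are secondary outcomes of a feasibility pilot. All of this stands, and it limits the point to analysis and reporting.

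A reader might infer more than the documents support:

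- **That the entry rule fails to enrich.** It multiplies each rate by 1/E. Depression rises from 24% to 27-37% in the simulations.
- **That members below threshold cannot show a decrease.** A clinical threshold is not the bottom of the scale. They have less room to fall, not none.
- **That a decrease is tested on every scale, with most participants below threshold on each.** Only the distress measures are meant to fall, and the inference fails for anxiety.
- **That the effect shrinks by the share below threshold.** An assumed 0.5 SD effect would become 0.5 × 0.27 = 0.14 to 0.5 × 0.37 = 0.19 SD for depression. That requires zero effect below threshold, the worst case, and a separate depression outcome. The plan names HADS without saying total or subscale.

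The chi-squared tests leave room for a categorical outcome, but none is defined.

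**Conclusion.** The point holds as a weakness of analysis and reporting, not of validity. Most enrolled participants probably start below threshold on depression (63-73% below; 48-76% at the extremes) and on PTS (71-79% below), while about half or more start above it on anxiety. Section VI does not use the baseline scores and does not report the status that defined entry. The results are less precise estimates, an effect size that averages over an undescribed baseline mix, and no direct answer on prevention. The contrast between arms remains unbiased.

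The shares assume that the Section I rates carry over to this trial's population and screening cut-offs. The narrower ranges also rest on assumed correlations. That all participants are analysed together is inferred from silence, because no analysis population is stated.

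**What to change.** Keep the eligibility rule and amend Section VI:

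1. Compare the arms on HADS and PCL-S at post-intervention and at 3 months in all randomised participants, adjusted for the same scale's baseline score.
2. State the instruments and cut-offs used for entry screening. Report by arm, with confidence intervals and labelled descriptive, the proportion of dyads with at least one member above those cut-offs at post-intervention and at 3 months.
3. Optionally, show the adjusted differences separately for members above and below the cut-off at baseline, as description only.

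The cost is SAP wording and a few tables. HADS and PCL-S are already scheduled at all three time points in Section V, so no visits or participants are added. The drawback is imprecision. Item 2 carries a half-width of about 22-25 percentage points. In item 3, a 35% share above threshold on depression leaves about 0.35 × 30 ≈ 10 people per role per arm.

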Current management of ANIs does not meet the psychological needs of pts and cgs for 3 reasons⁴⁰⁻⁵¹. First, although recognition of the emotional burden associated with NICU admission has increased, and some NICUs have social workers available to assist pts and cgs, there are no formal screening methods for emotional distress routinely integrated in practice during hospitalization, when the primary focus is on medical care and survival; further, there are no formal evidence-based treatments integrated within the medical care. When social workers are included to help pts and cgs, the care is brief and occurs only during hospitalization. When referrals to mental health services are provided to families at discharge, few will access additional treatment due to burden associated with traveling outside of home. Second, psychosocial interventions available for ANI pts or cgs are limited in that they are delivered when symptoms are already chronic, address only one emotional illness (e.g., depression or anxiety or PTS), and/or are focused on a *single member* of the pt-cg dyad. Even interventions labeled as "dyadic," which include pts and cgs, typically address only the pts' needs and do not

focus on cg outcomes or on the dyad's interpersonal communication and bond/relationship^{12,52}. These interventions are not consistent with the *dyadic framework*²² which specifies that dyadic interventions should account for the interdependence between pt and cg psychosocial factors including their interpersonal bond by ensuring that both pts and cgs attend each session together, and by targeting improvement in outcomes for both pts and cgs. Third, most interventions are delivered using uniform protocols. However, the needs of ANI dyads are heterogeneous due to varying levels of post ANI impairment, identity of the cg, context and stage of life. A recent systematic review⁵² urged for the development of dyadic interventions that address the needs of *both* pts and cgs and are tailored to the specific needs of each ANI dyad.

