After enrollment, participants will complete study assessments. All subjects will be given baseline psychological and behavioral assessments that will assess depression, anxiety, PTS symptoms, and other psychological constructs. Assessments will be administered online, using the REDCap system. Subjects may choose to fill out these questionnaires on-site, or to fill them out at home on a personal computer or other Internet-equipped device. This assessment includes demographic information and a battery of psychological questionnaires. We will also collect information about important clinical variables including duration of acute hospitalization. All questionnaires are itemized below:

Administered at Baseline Only:

Demographics

Prior Mental Health History questions

Credibility Questionnaire

Administered at Baseline, Post-Intervention, and Follow-up:

Medical history information from LMR (i.e., prior ANI status, current psychotropic meds, comorbid medical conditions, etc.)

Post-Traumatic Stress Disorder Checklist (PCL-S)²⁹

Hospital Depression and Anxiety Scale (HADS)³⁰
 Measure of Current Status Part A (MOCS-A)³¹
 The Cognitive and Affective Mindfulness Scale (CAMS)³²
 World Health Organization Quality of Life (WHOQOL-BREF)³³
 Dyadic Relationship Scale (DRS)
 Experience in Close Relationships – Relationship Structure (ECR-RS)

Administered Post-Intervention and Follow-up Only:
 Client Satisfaction Questionnaire (CSQ-3)³⁴

The study staff will complete the following questionnaires to assess symptom severity for each patient at all 3 timepoints (baseline, post intervention and follow up):

Modified Rankin Scale (mRS)³⁵ [Pts only]
 Barthel Index³⁶ [Pts only]

After completing the baseline assessments, dyads will be randomized to either the newly developed psychosocial intervention or to treatment as usual.

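### Self-efficacy and social support are secondary outcomes with a between-arm hypothesis, but no questionnaire in the itemized battery is named for or assigned to either

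*Combined protocol and SAP*

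**What the plan says.** All references are to the combined protocol and SAP.

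- **Section II, closing paragraph on outcomes.** "Our secondary outcomes in this trial are: emotional distress, PTS, mindfulness, coping, social support, self-efficacy, and interpersonal bond". That is seven constructs.
- **Section II, Aim 2.** The aim covers "emotional distress [Hospital Anxiety and Depression Scale; HADS], Post Traumatic Symptoms (PTS) [PCL-S], resiliency variables (mindfulness, coping, social support and self-efficacy"), followed by interpersonal bond. Brackets give an instrument for distress and for PTS, and for nothing after them.
- **Section II, Aim 2 Hypothesis 2.** Relative to the educational control, the program is expected to bring a "more potent increase in resiliency variables (mindfulness, coping, social support, self-efficacy) and interpersonal factors (interpersonal bond"), with the gain lasting to the 3-month follow-up.
- **Section V, assessment schedule.** The battery is said to assess "depression, anxiety, PTS symptoms, and other psychological constructs", and the list opens with "All questionnaires are itemized below". The self-report scales given at all three timepoints are PCL-S, HADS, MOCS-A, CAMS, WHOQOL-BREF, DRS and ECR-RS. No target construct is stated for any of them.
- **Section V, post-treatment assessment.** The later battery repeats the baseline one and adds only the CSQ-3.
- **Section VI, third question.** The secondary outcomes are given as PCL-S, HADS and, collectively, *resiliency measures*, with no breakdown.

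**The concern.** A secondary outcome with a directional hypothesis needs a designated score. Here two declared outcomes have none at baseline, post-intervention or 3 months, in a schedule that presents itself as complete.

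What follows depends on an intention that the documents do not state:

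1. A listed scale or subscale was meant to serve. Data will then exist, but which scale and which scoring remain open after results are visible, so the comparison is not prespecified.
2. No listed scale covers the construct. That part of Hypothesis 2 then cannot be tested, and a baseline value not collected before randomisation cannot be obtained later.

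The constructs are not peripheral. Section V lists both among the skills the intervention teaches, and says the control omits the skills thought to drive improvement in distress. A proof of concept under Aim 2 would want to show movement in them.

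**Working it through.** The point is a matter of matching text, so each secondary outcome is set against Aim 2 and the Section V list.

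| Secondary outcome (Section II) | Instrument assigned in Aim 2 | Section V scale whose title fits | Status |
|---|---|---|---|
| Emotional distress | HADS | HADS | assigned |
| PTS | PCL-S | PCL-S | assigned |
| Mindfulness | none | CAMS | identifiable by title |
| Interpersonal bond | none | DRS or ECR-RS | plausible by title, none chosen |
| Coping | none | none | no instrument |
| Social support | none | none | no instrument |
| Self-efficacy | none | none | no instrument |

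Count: 2 + 1 + 1 + 3 = 7. The three without an instrument are 3 of the 4 resiliency variables and 3 of the 5 constructs in Hypothesis 2 (four resiliency variables plus bond).

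The bond row is only plausible. It relies on Section I treating bond and relationship together, in "interpersonal communication and bond/relationship", and on two scale titles that refer to relationships.

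**Does any other text supply the link?**

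- *Section I, description of the program.* It defines social support as "empathetic interpersonal interactions that meet one’s emotional and functional needs" and self-efficacy as "perceived ability to adapt under adversity", but names no scale for either. The first definition could overlap with DRS or ECR-RS. Those are also the only title candidates for interpersonal bond, and nothing divides them between the two outcomes.
- *Section V, remaining items.* Demographics, mental health history, the credibility and satisfaction questionnaires, medical history and the two staff-completed functional scales are not named for these constructs.
- *Leftover scales.* MOCS-A and WHOQOL-BREF match no declared secondary outcome by title. The documents do not describe their content, so neither can be assigned from the text.
- *Section VI.* The collective term does not say which scales it includes.
- *Section X.* A self-efficacy scale (entry 69) and social-support measures (entries 70 and 72) appear in the reference list, but the body text does not cite them and the battery does not include them.

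**Sample size.** Section VI needs 30 dyads per arm after 25% attrition: 30 / (1 − 0.25) = 40 per arm, which reproduces the plan's 40 per arm and 80 in total. The figure does not depend on these outcomes.

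**The case against.** The best reply is that this is under-specification, not contradiction. Section V never says that self-efficacy or social support goes unmeasured; it refers openly to other constructs and gives no target for any scale. Section VI speaks of resiliency measures in the plural, although only CAMS matches a resiliency variable by title, and says measures were chosen to fit the theoretical frameworks. Both suggest that further listed scales were meant to serve. On that reading the sponsor need only write the mapping down.

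Much of this stands. A reader might infer that the two constructs are certainly unmeasured; the documents do not support that, because MOCS-A, WHOQOL-BREF, DRS or ECR-RS might be intended to cover them. A reader might equally assume that MOCS-A is the coping measure, or that entries 69, 70 and 72 reveal the intended scales; no text says either. What the reply does not do is name a scale or a score. A plural noun is not an assignment, and the schedule's claim to be complete leaves no other place for the assignment to be found.

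The citation numbers on the Section V list (29 to 36) lead to clinical and caregiver papers, not to sources for the scales. Sources for several of the scales sit elsewhere in Section X, for example MOCS at entry 71. That is a separate clerical fault and is not evidence on this point.

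It is also fair to say that this is a feasibility pilot. Its primary outcomes lie in Aim 1, and Section VI directs effect-size estimation at distress, which has an assigned scale.

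**Conclusion.** The concern holds as a missing link from outcome to instrument. Self-efficacy and social support are declared secondary outcomes with a directional between-arm hypothesis and have no designated score. Coping is in the same position, and interpersonal bond has two candidates with no choice made.

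This rests on the Section V list being complete, as it says, and on reading scale titles only, without outside knowledge of scale content. A figure is missing from the supplied text, but it sits in the description of the intervention, and the finding rests on the text list.

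Whether data on the two constructs would exist cannot be settled from the documents. The plural wording in Section VI makes an unstated assignment somewhat more likely than a true gap, but does not establish it. Either way, this part of Hypothesis 2 cannot be tested as prespecified. The point should be corrected, but its weight is limited: Aim 1, Aim 2 Hypothesis 1 and the sample size are unaffected.

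**What to change.** Add one table that maps each of the seven secondary outcomes to an instrument, a score and the timepoints, and fix it before outcome data are seen. For self-efficacy and for social support, do one of the following:

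- **(a) Add a scale.** Put a named scale for the construct into the Section V schedule at all three timepoints, and state how any dyads already enrolled without a baseline score are handled. Cost: if done for both constructs, 2 scales × 3 assessments = 6 further administrations per participant, plus a protocol amendment. The burden should be small, though scale lengths are not given.
- **(b) Designate a listed scale.** If a scale or subscale in the battery truly covers the construct, name it and state its scoring. Cost: wording.
- **(c) Remove the construct** from Hypothesis 2 and from the Section II outcome list. Cost: a protocol amendment that drops a declared secondary outcome, which is a substantive change.

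In the same table, designate the instrument for coping, without presuming MOCS-A, and a single scale for interpersonal bond. The citation numbers on the Section V list can be corrected separately.
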